17.5 Follow-Up for Serious Adverse Events

All related SAEs should be followed to their resolution, until the study participant is lost to follow-up, the start of a new treatment, or until the study investigator assesses the event(s) as stable or irreversible. New information will be reported when it is received.

17.6 Unanticipated Problems

An Unanticipated Problem (UP) is any incident, experience, or outcome that meets all of the following criteria:

- Unexpected (in terms of nature, severity, or frequency) given:
 - The research procedures that are described in the study-related documents, including study deviations, as well as issues related to compromise of participant privacy or confidentiality of data.
 - o The characteristics of the participant population being studied.
- Related or possibly related to participation in the research (possibly related means there is a reasonable possibility that the incident, experience, or outcome may have been caused by the procedures involved in the research).
- Suggests that the research places participants or others at a greater risk of harm (including physical, psychological, economic, or social harm) than was previously known or recognized or if in relation to an AE is deemed Serious per Section 17.4.

17.6.1 REPORTING UNANTICIPATED PROBLEMS

Unanticipated problem reporting will begin at the time of participant consent. The Reportable New Information (RNI) Form will be submitted to the CRS Quality Assurance (QA) Office within 1

APPROVED RPCI IRB 1/5/2024

Roswell Park Protocol No.: I 67918

business day of becoming aware of the Unanticipated Problem. After review, CRS QA Office will submit the RNI to the IRB.

When becoming aware of new information about an Unanticipated Problem, submit the updated information to CRS QA Office with an updated Reportable New Information Form. The site Investigator or designated research personnel will report all unanticipated problems, whether related or unrelated to the investigational agent(s) to the IRB in accordance with their local institutional guidelines.

17.7 FDA Reporting

When Roswell Park is the IND holder the following describes the FDA reporting requirements by timeline for AEs and new safety findings that meet the criteria outlined below:

Within 7 Calendar Days

Any adverse event that meets **ALL** the following criteria:

- Related or possibly related to the use of the study drug;
- Unexpected; and
- Fatal or life-threatening.

Within 15 Calendar Days

Any adverse event that meets **ALL** the following criteria:

- Related or possibly related to the use of the study drug;
- Unexpected; and
- Serious but not fatal or life-threatening;

Or, meets **ANY** of the following criteria:

- A previous adverse event that is not initially deemed reportable but is later found to fit the criteria for reporting (report within 15 days from when event was deemed reportable).
- Any findings from other studies, including epidemiological studies, pooled analysis of
 multiple studies, or other clinical studies conducted with the study drug that suggest a
 significant risk in humans exposed to the drug.
- Any findings from animal or in vitro testing that suggest a significant risk for human participants including reports of mutagenicity, teratogenicity, or carcinogenicity or reports of significant organ toxicity at or near the expected human exposure.
- Any clinically important increase in the rate of occurrence of a serious, related or possibly related adverse event over that listed in the protocol or investigator brochure.

Sponsors are also required to identify in IND safety reports, all previous reports concerning similar adverse events and to analyze the significance of the current event in the light of the previous reports.

17.8 Investigator Reporting: Notifying the Manufacturer of Porfimer Sodium

Investigators MUST report (within 1 business day), upon becoming aware, to Pinnacle Biologics, Inc. ANY Serious Adverse Events, whether or not they are considered related to the investigational agents using the forms supplied by Pinnacle.

Pinnacle reporting contact: fax ([contact]) or email ([contact]).

17.9 Reporting Process

The principal investigator or designee will complete and submit a FDA Form 3500A MedWatch for any event that meets the above criteria. Forms will be submitted to the CRS QA Office via email to [contact].

18.0 Data Management and Confidentiality

18.1 Data Collection

Full build studies are managed by Roswell Park CRS Data Management for analysis by Roswell Park Biostatisticians. All electronic case report form (eCRF) data are captured for these studies.

Clinical data management activities are performed using CTMS and EDC systems that enable the collection, cleaning and viewing of clinical trial data. CRS Clinical Data manages, designs and develops the study-specific database Once the database design is approved by the Investigator, Statistician, and Clinical Research Coordinator, the database is put into Production and data entry can begin. Data can be entered and changed only by those with the rights to do so into the eCRFs.

18.2 Maintenance of Study Documents

Essential documents will be retained per Roswell Park policy for 6 years from the study termination date. These documents could be retained for a longer period, however, if required by the applicable local regulatory requirements or by an agreement with Roswell Park.

18.3 Revisions to the Protocol

Roswell Park may make such changes to the protocol as it deems necessary for safety reasons or as may be required by the U.S. FDA or other regulatory agencies. Revisions will be submitted to the IRB/ERC for written approval before implementation.

18.4 Termination of the Study

It is agreed that, for reasonable cause, either the Roswell Park Investigators or the Sponsor, may terminate this study, provided a written notice is submitted within the time period provided for in the Clinical Trial Agreement. In addition, Roswell Park may terminate the study at any time upon immediate notice if it believes termination is necessary for the safety of participants enrolled in the study.

18.5 Confidentiality

Any data, specimens, forms, reports, video recordings, and other records that leave the site will be identified only by a participant identification number (Participant ID, PID) to maintain confidentiality. All records will be kept in a limited access environment. All computer entry and

networking programs will be done using PIDs only. Information will not be released without written authorization of the participant.

19.0 Statistical Plan

This is a Phase 1 trial. The primary objective of the Phase 1 component is to test the safety of porfimer sodium mediated I-PDT in patients with locally advanced or recurrent HNC who are not candidates for standard or salvage surgery or radiotherapy.

19.1 Sample Size Determination

The maximum sample size is 12 patients. The actual sample size depends on the unknown dose-toxicity profile of the treatment, see section 10.14 for the dose escalation scheme.

19.2 Demographics and Baseline Characteristics

Descriptive statistics such as frequencies and relative frequencies will be computed for all categorical variables. Numeric variables will be summarized using simple descriptive statistics such as the mean, standard deviation and range. A variety of graphical techniques will also be used to display data such as histograms, boxplots, scatterplots, etc.

19.3 Safety Analysis

The safety will be determined by recording the occurrence of SAE during the first 30 days post first SOC treatment day (or last I-PDT day if no therapeutic SOC is given) using the revised NCI Common Terminology Criteria for Adverse Events (CTCAE) version 5.0. Sequential boundaries will be used to monitor the SAE rate (64). The accrual will be halted if excessive numbers of SAEs are seen.

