8.0 Study Endpoints

8.1 Primary Endpoints

Phase 1:

o The safety will be determined by recording the occurrence of AE during the first 30 days post final I-PDT day, using the revised NCI Common Terminology Criteria for Adverse Events (CTCAE) version 5.0.

Exploratory Endpoint

Objective target tumor response rates will be assessed according to RECIST v1.1 at 12 ± 2 weeks post I-PDT as described in section 16.2.

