10.3 Definition of Dose-Limiting Toxicity

Dose Limiting Toxicities will include:

Any adverse events (AEs) that are \geq grade 4 that are possibly, probably, or definitely related to the I-PDT, by recording the occurrence of AE during the first 30 days post final I-PDT treatment using the revised the National Cancer Institute (NCI) Common Terminology Criteria for Adverse Events version 5.0 (CTCAE v5.0). Dose Limiting Toxicities will be evaluated for 30 days post final I-PDT day.

If participants experience DLTs, further I-PDT sessions will be held until DLT resolution as well as after porfimer sodium clearance.

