10.4 Dose Escalation/Finding Schema

The FDA approved porfimer sodium dose (2 mg/kg) will not change. We will aim to deliver light fluence rate of ≥ 8.6 mW/cm² and fluence of ≥ 45 J/cm² to 100% of the CTV (dose level 1), as much as possible. Dose level -1 will ≥ 5.0 mW/cm² and fluence of ≥ 45 J/cm² to 100% of the CTV.

Table 2. The study plan for finding optimal fluence rate in I-PDT with Photofrin in patients with LAHNC.			
Dose Level Number of patients with DLT at a given dose level		Decision rules	
Dose Level 1 (Starting): The maximum fluence rate, scaled for	0 out of 3	Enter 3 patients at Dose Level 1 : The laser fluence rate and fluence, scaled for human, which induced maximum photoreaction in the animal models	
human, which induced effective	1 out of 3	Enter 3 more patients at this Dose Level .	

photoreaction in the animal models.	≥2	Enter 3 patients at Dose Level -1 : The laser fluence rate and fluence, scaled for human, which induced minimal toxicity in the animal models.
	≤ 1 out of 6	This is generally the recommended Phase II dose rate/dose. At least 6 patients must be entered at the recommended Phase II dose.

In participants where their tumors may require more than one course of I-PDT for complete effective illumination of the CTV, up to three sessions of I-PDT may be performed, at the discretion of the treating physician. The FDA approves to administer up to three courses of PDT with Photofrin® each separated by at least 30 days in the treatment of esophageal and endobronchial cancer (http://www.photofrin.com/wp-content/uploads/2013/02/prescribing-info.pdf.). Therefore, treatment sessions in this study will be conducted at least 30-days apart. The porfimer sodium dose (2 mg/kg) will remain the same.

See Appendix D 1 for the Dose Escalation Schedule of Events. The date of the last I-PDT course will be used to determine the scheduling of the follow up SoC related to this study.

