14.0 Potential Benefits to Subjects

For subjects that will have partial or complete response to I-PDT, the potential benefits include reduction in tumor related side effects (such as bleeding, pain, and dysphagia). Subjects that do not respond to I-PDT may not benefit from this treatment. In addition it has been shown, in other diseases sites, that PDT can improve OS and PFS when added to SoC therapy. Thus, it is possible that subjects that will respond to the experimental arm (I-PDT + SoC) will have increased OS and PFS. There is no guarantee of the outcome nor is it possible to predict whether or not the subject will respond to porfimer sodium-mediated I-PDT.

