 - 10. If possible, intraoperative CT (such as O arm) or another radiological imaging (e.g. C-arm) will be used to image the catheters in the tumor.
 - 11. Refer to Section 10.2.1.
 - 12. Medications ongoing within 1 week prior to porfimer sodium injection.
 - 13. AE reporting period will be for 30 days \pm 2 days post first SOC treatment.
 - 14. First SOC treatment day of I-PDT day if no therapeutic SOC treatment is administered.
 - 15. Refer to Section 11.6f patient doesn't come in or quality of life is missed, may be done via telephone.
 - 16. In the event that the tumor size is such that treating the entire tumor could cause a health risk to the patient, the current I-PDT course will be broken up into session/s. We will illuminate one part of the tumor on the day of I-PDT and another part/s of the tumor in additional I-PDT session/s within 14 days after the initial I-PDT session, at the discretion of the treating physician. If

- an I-PDT course is broken up into I-PDT sessions, the I-PDT dosage for each session will remain the same as though sessions were not broken up as dosing is dependent on number of fibers received per session. The patient will not need to receive additional doses of porfimer sodium if having additional I-PDT sessions within 14 days after the previous I-PDT session as porfimer sodium is expected to be in the tumor for at least 30 days.
- 17. Another (one or two, total of three) laser light treatment(s) only (no additional drug) within 2-3 weeks of the initial administration of Photofrin.
- 18. Patient may receive a second complete I-PDT treatment that will include drug and light administration. It will be at the discretion of the treating physician to administer this additional treatment. Another CT (charged to the study if it is not SoC) will be done, and all tests will be conducted before and after additional treatment, according to the same schedule parameters as the initial treatment.

Appendix D 1 Schedule of Procedures and Observations (Only for Dose Escalation later I-PDT Sessions if Deemed Necessary by Physician)**

Evaluation	Repeat of Initial Tests and Procedures ^A	Pre- Operative	Day of Treatment	1-week Post- treatment	Clinic Visit	Post- Treatment	Follow- Up
Physical Exam/ Vital signs ^B & pain assessment using a verbal score 0-10	X			X	X	X	X
Hematology ^C and Chemistry ^D	X			X	X	X	
Research Blood Draws ^E			X	X	X	X	X
Pregnancy Test (Urine)	X						
ECOG Performance Status	X		X	X	X	X	X
UW-QoLQ v. 4 ^p	X			X	X	X	X

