 - F. If required per physician's discretion, standard tumor staging performed within 4 weeks, and at least 14 business days prior to following I-PDT. If possible, the imaging will include temporary fiducial markers that will be affixed to skin. Refer to Section 11.2.
 - G. CT scans at 10 to 12 weeks post I-PDT and as clinically indicated following the NCNN 2018 guidelines.
 - H. If tumor results determine porfimer sodium infusion is needed for later 2nd and 3rd I-PDT sessions, infusion will occur 48 hours ±8 h prior to illumination. Vitals are to be taken immediately after injection and after 15 minutes.
 - I. If possible, intraoperative CT (such as O arm) or another radiological imaging (e.g. C-arm) will be used to image the catheters in the tumor.
 - J. Refer to Section 10.2.1.
 - K. Medications ongoing within 1 week prior to illumination.
 - L. Refer to Section 10.2.1.
 - Li. The later 2nd and 3rd I-PDT study treatments total as per the physician's discretion are at least 30 days apart from each other (see Section 10.4). For additional I-PDT treatments that are 30 days from the previous that require an additional dosage of porfimer sodium the porfimer sodium (2mg/kg) is administered 48 hours prior to illumination.
 - M. AE reporting period will be for 30 days \pm 2 days post first SOC treatment.
 - Oi. Since there may be up to three I-PDT courses, at least 30 days apart (see Section 10.4), per the physician's discretion, adverse events review of previous study treatments are reviewed prior of the next additional I-PDT.
 - N. In Phase 1, patients are off treatment/on follow up as clinically indicated 30 days after the last I-PDT.
 - O. Refer to Section 11.6 if patient doesn't come in or quality of life is missed, may be done via telephone.

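### Section 19.3 determines safety from SAEs in the 30 days after first standard-of-care treatment, whereas the primary endpoint in 8.1 is AEs in the 30 days after final I-PDT

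*Combined protocol and SAP*

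**What the plan says.** Section 8.1 determines safety by "recording the occurrence of AE during the first 30 days post final I-PDT day", graded by CTCAE v5.0. Section 10.3 uses the same clock for DLTs, which are related AEs of grade 4 or higher: "Dose Limiting Toxicities will be evaluated for 30 days post final I-PDT day".

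Section 19.3 uses a different event and a different clock: "SAE during the first 30 days post first SOC treatment day (or last I-PDT day if no therapeutic SOC is given"). The last I-PDT day is only the fallback.

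The SOC anchor recurs in the schedules:

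- Appendix D note 13, on the Adverse Events row: "AE reporting period will be for 30 days", plus or minus "2 days post first SOC treatment".
- Appendix D note 14, on the column headed 30-Day Post I-PDT: "First SOC treatment day of I-PDT day if no therapeutic SOC treatment is administered".
- Appendix D 1: the same AE-period text as note 13, listed as note M. The D 1 note letters are offset from the table. Its Adverse Events row carries O, and M sits on Concomitant Medications.

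Sections 17.3 and 17.4.1 use neither clock cleanly. AE and SAE reporting runs to 30 days after the last intervention, or stops when a new treatment starts. Neither section says whether SOC is a new treatment.

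**The concern.** Safety of I-PDT is the primary objective, and 19.3 is the section that says how safety will be determined. Where it departs from 8.1, two analysts following the two sections could report different primary safety results for a participant who goes on to SOC. A clock that starts at SOC can pass over the days straight after I-PDT and take in days when chemotherapy, targeted therapy or immunotherapy is the more likely cause of an event. Section 19.3 also narrows the endpoint from all AEs to serious ones. The appendix notes repeat the anchor, so correcting 19.3 alone would leave the schedule in conflict with it.

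**Working it through.** The plan gives no figure for this mismatch, so there is none to reproduce. The check compares the two windows.

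**Inputs**

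- Endpoint window: days 0 to 30 after final I-PDT (8.1, 10.3).
- 19.3 window: 30 days from first SOC treatment.
- d: days from final I-PDT to first SOC treatment. The documents do not fix it.
- Assumed range d = 7 to 28. Appendix D note 2 puts the Clinic Visit on SOC day 1, and 11.5 puts the first post-operative clinic visit at 1 to 4 weeks. The range assumes that these are the same visit.
- d of 30 or more is also possible. D 1 note N, which may belong to the SOC row, has Phase 1 patients off treatment 30 days after the last I-PDT.
- Participants given SOC: 0 to 12, the maximum sample size (19.1).

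**Formulas**

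- Literal reading (days d to d + 30): endpoint days omitted = min(d, 30); endpoint days shared = max(30 − d, 0).
- Cumulative reading (days 0 to d + 30): none omitted; window length = d + 30; share of the window after SOC start = 30/(30 + d).

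| d | Literal: omitted of 30 | Shared with 8.1 | Cumulative: length | Share after SOC start |
|---|---|---|---|---|
| 7 | 7 (23%) | 23 | 37 | 30/37 = 81% |
| 14 | 14 (47%) | 16 | 44 | 30/44 = 68% |
| 21 | 21 (70%) | 9 | 51 | 30/51 = 59% |
| 28 | 28 (93%) | 2 | 58 | 30/58 = 52% |
| 30 or more | 30 (100%) | 0 | 60 or more | 50% or less |

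Under the cumulative reading, the d days past day 30 are all on SOC when d is 30 or less. For larger d, 30 of them are. The text of 19.3 does not say which reading is meant.

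If no SOC is given, both clocks start at the last I-PDT and the windows agree. Only SAE versus AE then differs.

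**Collection.** If SOC counts as a new treatment under 17.3 and 17.4.1, and starts before day 30, routine collection stops where the literal 19.3 window begins. The part of the 8.1 window left uncollected would be 30 − d days: 23, 16, 9 or 2 at d = 7, 14, 21 or 28. Section 17.4.1 still requires related SAEs after the follow-up period to be reported.

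**The case against.** Several counter-arguments have force.

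- **Early events are not lost from the study.** Section 17.3 collects from the start of intervention, and the Appendix D AE row is marked on the treatment day and at one week. Section 19.6 tabulates toxicities by grade for everyone treated, with no seriousness filter. This stands: a reader might infer that events between I-PDT and SOC disappear, and the documents do not support that. But 19.6 states no window, so it does not settle which count is the primary result.
- **Dose decisions are untouched.** A reader might infer that the recommended Phase 2 dose is at risk. It is not on this ground, because 10.3 and 10.4 use DLTs anchored on final I-PDT.
- **The SAE halt.** A reader might blame the window for an unworkable accrual halt. The halt has no stated boundary in 19.3, nor in 19.1 where 19.7 points. That is a separate problem, which a new anchor does not solve.
- **SOC may be rare or late.** Section 9.0 says only that these subjects would otherwise receive SOC. Section 10.4 states "The date of the last I-PDT course will be used to determine the scheduling of the follow up SoC related to this study", which may mean follow-up visits rather than therapy. Against that, 14.0 contemplates that "subjects that will respond to the experimental arm (I-PDT + SoC) will have increased OS and PFS", and D 1 has an SOC therapy row. SOC is therefore provided for, but its frequency and timing are unknown.
- **Leftover wording.** The SOC anchor may come from a controlled design. Section 16.2 still mentions a control arm, and 19.4 still has an I-PDT yes/no factor. That would explain the text, but it would still govern the analysis as written.
- **The 8.1 window also contains SOC days.** At d = 7, 23 of its 30 days (77%) follow SOC start, against 81% under the cumulative reading. This stands. Re-anchoring gives one consistent endpoint, not one free of SOC effects.

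**Conclusion.** The conflict is real and should be resolved before any safety analysis. Section 19.3 differs from 8.1 in event type for every participant, and in starting day for every participant given therapeutic SOC. Appendix D notes 13 and 14 and the D 1 AE-period text carry the same anchor.

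Per participant given SOC, the literal reading omits 7 to 28 of the 30 endpoint days if d is 7 to 28, and all 30 if d is 30 or more. The cumulative reading omits none and runs d days past day 30. The 7-to-28 range is an assumption, and the lower end is weakly supported because Appendix D has a separate one-week visit. A reader might take the percentages as shares of missed events, or conclude that the primary result must change. Neither follows. The documents give no event timing, and the result changes only if an event falls in the unshared days or a non-serious AE occurs.

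**What to change.** 1. Rewrite 19.3 so that the primary safety analysis is the 8.1 endpoint: AEs, with SAEs and DLTs as subsets, through 30 days after final I-PDT for every participant, whether or not SOC is given. Use the same window for the SAE monitoring count.
2. Decide where the window starts. Section 10.4 allows up to three sessions at least 30 days apart, so final I-PDT can fall 2 × 30 = 60 days or more after the first. If events between sessions are to count, start the window at first study treatment and make the same change in 8.1. Changing 19.3 alone would create a new mismatch.
3. Anchor Appendix D note 14 on final I-PDT, and reconcile notes 13 and M with 17.3. Report any AEs collected after day 30 separately.
4. State in 17.3 and 17.4.1 that starting SOC does not end AE or SAE collection inside the 30-day window.
5. Flag events with onset after SOC start.

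The cost is a wording amendment. If SOC would otherwise have stopped collection, it adds up to 23 collection days per participant at d = 7, falling to 2 at d = 28. Otherwise it adds none. The same 23 to 2 days on SOC remain inside the primary window, so some SOC-period events will be counted there. The onset flag and the attribution already recorded under 17.2.1 are the means of handling them.
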